3. ENDPOINTS AND BASELINE VARIABLES: DEFINITIONS AND CONVENTIONS

3.1. Primary Endpoints

3.1.1. Safety Endpoints

3.1.2. Primary Safety Endpoints

- Local reactions (redness, swelling, and pain at the injection site) within 7 days after administration
- Systemic events (fever, headache, fatigue, muscle pain, and joint pain) within 7 days after administration
- AEs within 1 month after administration
- SAEs within 1 month after administration

3.1.2.1. Local Reactions and Systemic Events

The local reactions, including redness, swelling, and pain at the injection site, and the systemic events, including fever, fatigue (tiredness), headache, muscle pain, and joint pain, are reported in the e-diary from Day 1 through Day 7 after administration, where Day 1 is the day of administration. The e-diary entries from the participant will be the primary data source for these events. However, any events related to administration that are considered local reactions or systemic events starting within 7 days after administration, that happen to be entered on the AE CRF, will be consolidated with e-diary data, and included in the reactogenicity summary. This section describes derivations with details for the assessment of the reactogenicity data: severity level, duration, and onset day.

Severity and Maximum Severity

The definitions for reactogenicity severity collected from the e-diary and from AEs are described in [Appendix 2](#).

For each local reaction or systemic event after administration, the maximum severity grade will be derived for the collection period (Day 1 through Day 7, where Day 1 is the day of administration) as follows:

maximum severity grade = highest grade (maximum severity) within 7 days after administration (Day 1 through Day 7) among severity grades reported for that local reaction or systemic event

Temperatures recorded in degrees Fahrenheit will be programmatically converted to degrees Celsius first for reporting. Fever will be grouped into ranges for the analysis according to Table 4. Maximum temperature range over the period from Day 1 through Day 7 will be mapped into the ranges described in Table 4 for summary of maximum temperature. For fever reported on the AE CRF within 7 days after administration, mild fever will be grouped in the $\geq 38.0^{\circ}\text{C}$ to 38.4°C range, moderate fever will be grouped in the $>38.4^{\circ}\text{C}$ to 38.9°C range, and severe fever will be grouped in the $>38.9^{\circ}\text{C}$ to 40.0°C range (unless specifically noted to be $>40.0^{\circ}\text{C}$ in an unplanned visit contact or noted on the AE CRF).

Table 4. Ranges for Fever

$\geq 38.0^{\circ}\text{C}$ to 38.4°C
$>38.4^{\circ}\text{C}$ to 38.9°C
$>38.9^{\circ}\text{C}$ to $40.0^{\circ}\text{C}^{\text{a}}$
$>40.0^{\circ}\text{C}^{\text{a}}$

Note: Fever is defined as temperature $\geq 38.0^{\circ}\text{C}$ based on e-diary data or indicated on the AE CRF within 7 days after administration.

a. Participants reporting a fever $>102.0^{\circ}\text{F}$ ($>38.9^{\circ}\text{C}$) will be prompted to contact the study site.

[REDACTED]

[REDACTED]

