6.4.2. Blinding of Site Personnel

Investigators and other site staff will be unblinded to participants' assigned study intervention.

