8.3.2.1. Local Reactions

From Day 1 through Day 7 following study intervention administration at Visit 1, where Day 1 is the day of study intervention administration, participants will be asked to assess redness, swelling, and pain at the injection site and to record the symptoms in the e-diary in the evening. Redness and swelling will be measured and recorded in measuring device (caliper) units (range: 1 to 21+) and then categorized during analysis as mild, moderate, or severe based on the grading scale in [Table 2](#). Measuring device units can be converted to centimeters according to the following scale: 1 measuring device unit = 0.5 cm. Pain at the study intervention injection site will be assessed by the participant as mild, moderate, or severe according to the grading scale in [Table 2](#). The participant will be prompted to contact the investigator if he/she experiences a severe (Grade 3 or above) local reaction to assess the reaction and perform an unscheduled assessment or visit as appropriate. Only an investigator is able to classify a participant's local reaction as Grade 4, after physical examination of the participant or documentation from another medically qualified source (eg, emergency room

or hospital record). If a participant experiences a Grade 4 local reaction, the investigator must immediately notify the sponsor. Site staff will educate the participants regarding signs and symptoms that would prompt site contact. Grade 4 reactions will be collected as AEs on the CRF. The event will be graded using the AE intensity grading scale (Section 10.3.3).

The procedure for notification of the sponsor is provided in the investigator site file or equivalent.

Table 2. Grading Scales for Local Reactions

	Mild Grade 1	Moderate Grade 2	Severe Grade 3^a	Grade 4^b
Redness	5 to 10 measuring device units = >2.0 to 5.0 cm	11 to 20 measuring device units = >5.0 to 10.0 cm	>20 measuring device units = >10.0 cm	Necrosis or exfoliative dermatitis
Swelling	5 to 10 measuring device units = >2.0 to 5.0 cm	11 to 20 measuring device units = >5.0 to 10.0 cm	>20 measuring device units = >10.0 cm	Necrosis
Pain at injection site	Does not interfere with activity	Interferes with activity	Prevents daily activity ^c	Emergency room visit or hospitalization for severe injection site pain

Note: If the size of the redness and/or swelling falls between 2 measuring device units, the higher measuring device unit number will be recorded in the e-diary.

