- The investigator will attempt to establish a diagnosis of the event based on signs, symptoms, and/or other clinical information. Whenever possible, the diagnosis (not the individual signs/symptoms) will be documented as the AE or SAE.

Assessment of Intensity

The investigator will make an assessment of intensity for each AE and SAE reported during the study and assign it to 1 of the following categories:

- Mild: A type of AE that is usually transient and may require only minimal treatment or therapeutic intervention. The event does not generally interfere with usual ADL.
- Moderate: A type of AE that is usually alleviated with additional specific therapeutic intervention. The event interferes with usual ADL, causing discomfort, but poses no significant or permanent risk of harm to the research participant.
- Severe: A type of AE that interrupts usual ADL, or significantly affects clinical status, or may require intensive therapeutic intervention.

GRADE	If required on the AE page of the CRF, the investigator will use the adjectives MILD, MODERATE, SEVERE to describe the maximum intensity of the AE. For purposes of consistency, these intensity grades are defined as follows:	
1	MILD	Does not interfere with participant's usual function.
2	MODERATE	Interferes to some extent with participant's usual function.

PFIZER CONFIDENTIAL

3	SEVERE	Interferes significantly with participant's usual function.
An event is defined as “serious” when it meets at least 1 of the predefined outcomes as described in the definition of an SAE, NOT when it is rated as severe.		

Assessment of Causality	
• The investigator is obligated to assess the relationship between study intervention and each occurrence of each AE or SAE. The investigator will use clinical judgment to determine the relationship.	• A “reasonable possibility” of a relationship conveys that there are facts, evidence, and/or arguments to suggest a causal relationship, rather than a relationship cannot be ruled out.
• Alternative causes, such as underlying disease(s), concomitant therapy, and other risk factors, as well as the temporal relationship of the event to study intervention administration, will be considered and investigated.	• The investigator will also consult the IB and/or product information, for marketed products, in their assessment.

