• For each AE or SAE, the investigator must document in the medical notes that they have reviewed the AE or SAE and have provided an assessment of causality.	• There may be situations in which an SAE has occurred and the investigator has minimal information to include in the initial report to the sponsor. However, it is very important that the investigator always make an assessment of causality for every event before the initial transmission of the SAE data to the sponsor.
• The investigator may change their opinion of causality in light of follow-up information and send an SAE follow-up report with the updated causality assessment.	• The causality assessment is one of the criteria used when determining regulatory reporting requirements.
• If the investigator does not know whether or not the study intervention caused the event, then the event will be handled as “related to study intervention” for reporting purposes, as defined by the sponsor. In addition, if the investigator determines that an SAE is associated with study procedures, the investigator must record this causal relationship in the source documents and CRF, and report such an assessment in the dedicated section of the Vaccine SAE Reporting Form and in accordance with the SAE reporting requirements.	

Follow-Up of AEs and SAEs

- The investigator is obligated to perform or arrange for the conduct of supplemental measurements and/or evaluations, as medically indicated or as requested by the sponsor, to elucidate the nature and/or causality of the AE or SAE as fully as possible. This may include additional laboratory tests or investigations, histopathological examinations, or consultation with other healthcare providers.
- If a participant dies during participation in the study or during a recognized follow-up period, the investigator will provide Pfizer Safety with a copy of any postmortem findings, including histopathology.
- New or updated information will be recorded in the originally submitted documents.
- The investigator will submit any updated SAE data to the sponsor within 24 hours of receipt of the information.

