2.2. Study Objectives, Endpoints, and Estimands

The estimands corresponding to each primary, secondary, [REDACTED] objective are described in [Table 2](#). The estimands to evaluate the immunogenicity objectives are based on evaluable populations (see [Section 4](#) for definition). These estimands estimate the study intervention effect in the hypothetical setting where participants follow the study schedules and protocol requirements as directed. Missing serology results will not be imputed.

Table 2. List of Primary, Secondary, and Exploratory Objectives, Endpoints, and Estimands

Objectives	Endpoints	Estimands
Primary:	Primary:	Primary:
To describe the safety profile of [REDACTED] candidates in adults 18 through 49 years of age	
 Prompted local reactions (redness, swelling, and pain at the injection site) Prompted systemic events (fever, headache, fatigue, muscle pain, and joint pain) AEs SAEs 	
In participants receiving the study intervention from each group, the percentage of participants reporting:
 
 Local reactions within 7 days after administration Systemic events within 7 days after administration AEs within 1 month after administration SAEs within 1 month after administration
Secondary:	Secondary:	Secondary:
To describe the immune responses elicited by the [REDACTED] candidates	
 OPA titers [REDACTED] 	
In participants complying with the key protocol criteria (evaluable participants) from each group:
 
 [REDACTED] OPA GMTs 1 month after administration
[REDACTED]	[REDACTED]	[REDACTED]

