6.1.2. Adverse Events**6.1.2.1. Main Analysis**

- Estimand: The percentage of participants reporting AEs from study intervention administration through 1 month after administration ([Section 2.2](#)).
- Analysis set: Safety population ([Section 4](#)).
- Analysis time point: From the study intervention administration through 1 month after administration.
- Analysis methodology: Descriptive statistics ([Section 5.2.1](#)).
- Reporting results: AEs will be categorized according to MedDRA terms. Descriptive summary statistics (counts, percentages, and associated Clopper-Pearson 95% CIs) will be provided for any AEs, by each SOC and each PT within the SOC for each group.

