Appendix 2. Reactogenicity Data Consolidation

For reactogenicity collected in the e-diary, redness and swelling will be measured and recorded in measuring device (caliper) units, and then categorized during analysis as mild, moderate, or severe based on the grading scale in Table 5. Measuring device units can be converted to centimeters according to the following scale: 1 measuring device unit = 0.5 cm. Pain at the injection site will be assessed by the participant as mild, moderate, or severe according to the grading scale in Table 5. The systemic events of fatigue (tiredness), headache, muscle pain, and joint pain will be assessed by participants as mild, moderate, or severe according to the grading scale in Table 6. Grade 4 reactions and events, which can only be classified by an investigator, will be collected as an AE on the CRF. For reactogenicity collected in the AE CRF, the grading scales will be based on the AE intensity scale in Table 7. If a local reaction or systemic event is captured in more than 1 data source, eg, e-diary, unplanned assessments, and/or AE CRF, the highest grade will be used in the safety summary analysis.

Table 5. Grading Scales for Local Reactions Collected From the E-Diary

Local Reaction	Mild Grade 1	Moderate Grade 2	Severe Grade 3 ^a	Grade 4 ^b
Redness	5 to 10 measuring device units = >2.0 to 5.0 cm	11 to 20 measuring device units = >5.0 to 10.0 cm	>20 measuring device units = >10.0 cm	Necrosis or exfoliative dermatitis
Swelling	5 to 10 measuring device units = >2.0 to 5.0 cm	11 to 20 measuring device units = >5.0 to 10.0 cm	>20 measuring device units = >10.0 cm	Necrosis
Pain at injection site	Does not interfere with activity	Interferes with activity	Prevents daily activity ^c	Emergency room visit or hospitalization for severe injection site pain

Abbreviation: CRF = case report form.

Note: If the size of the redness and/or swelling falls between 2 measuring device units, the higher measuring device unit number will be recorded in the e-diary.

- Participants experiencing Grade 3 local reactions are required to contact the investigator site. In the event that the participant does not call, the investigator will call the participant.
- Grade 4 assessment should be made by the investigator; Grade 4 local reactions will not be collected in the e-diary but will be collected as AEs on the CRF. The intensity of the local reaction should be graded using the AE intensity grading scale.

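### Minor: the SAP attaches a causality condition to AE-CRF events entering the primary reactogenicity percentages; diary entries, the estimand and the SAP's own fever and highest-grade rules carry none

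*SAP*

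**What the plan says.** **Entry rule.** SAP 3.1.2.1 makes participants' e-diary entries the primary source for local reactions and systemic events. It then brings into the reactogenicity summary "any events related to administration that are considered local reactions or systemic events starting within 7 days after administration" that were entered on the AE CRF. No causality condition is placed on diary entries.

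**Estimand.** SAP Table 2 has none either: "In participants receiving the study intervention from each group, the percentage of participants reporting" local reactions, and likewise systemic events, within 7 days.

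**Related rules in the same SAP.** The AE-CRF fever rule in 3.1.2.1 and the note to SAP Table 4 count fever shown on the AE CRF within 7 days, with no mention of cause. Appendix 2 uses the highest grade when an event appears in more than one source, again with no mention of cause.

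**Who judges cause.** Protocol 10.3.3 says of the causality assessment: "The investigator will use clinical judgment to determine the relationship". Protocol 6.4.2 says: "Investigators and other site staff will be unblinded to participants' assigned study intervention".

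**Grade 4.** Under Protocol 8.3.2 and SAP Appendix 2, Grade 4 reactions and events are recorded on the AE CRF and never in the diary.

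**Size.** Protocol 8.3.2.1 gives the diary scale: "Redness and swelling will be measured and recorded in measuring device (caliper) units (range: 1 to 21" or more). SAP Table 5 starts Grade 1 redness and swelling at "5 to 10 measuring device units = >2.0 to 5.0 cm". Reactogenicity from the AE CRF is graded on SAP Table 7, which concerns interference with usual function and has no size criterion.

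**The concern.** One primary percentage has two entry rules. A headache typed into the diary counts whatever its cause. The same headache recorded only on the AE CRF counts, on the natural reading, if it is judged related. That judgment is made with the assigned group known, in a trial comparing new candidates with licensed controls. It also reaches Grade 4 events, the most severe category, because the AE CRF is their only route into the summary.

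The SAP is also not consistent with itself. A programmer following 3.1.2.1 literally could filter headache by causality and leave fever unfiltered.

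A second, smaller asymmetry concerns redness and swelling. The diary needs more than 2.0 cm for a grade and the AE CRF needs no size at all, so the form used can decide whether a small reaction counts.

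**Working it through.** **1. The rules side by side**

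| Rule | Causality condition |
|---|---|
| Diary entries (SAP 3.1.2.1) | none |
| Estimand (SAP Table 2) | none |
| AE-CRF local reactions and systemic events (SAP 3.1.2.1) | related to administration |
| AE-CRF fever (SAP 3.1.2.1, Table 4 note) | not repeated |
| Highest grade across sources (SAP Appendix 2) | not repeated |

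The conflict affects grade as well as counting. Take a participant with a mild diary headache and a severe AE-CRF headache judged unrelated. Under 3.1.2.1 the AE-CRF record stays out and the maximum is mild. Under Appendix 2 the maximum is severe.

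**2. The plan's own calculation.** Protocol Table 5 gives the chance of at least one event in a group of 45 as 1 − (1 − p)^45.
- p = 2%: 1 − 0.98^45 = 59.7%. The table shows 59.7%.
- p = 5%: 1 − 0.95^45 = 90.1%. The table shows 90.1%.

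The other three rows (3%, 4%, 6%) also reproduce: 74.6%, 84.1%, 93.8%.

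**3. Effect of one participant.** With 45 per group, each participant counted or not counted moves a percentage by 1/45 = 2.2 points. Clopper-Pearson 95% limits, the SAP 5.2.1 method:

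| Count | Percentage | 95% CI |
|---|---|---|
| 0/45 | 0% | 0 to 7.9 |
| 1/45 | 2.2% | 0.1 to 11.8 |
| 2/45 | 4.4% | 0.5 to 15.1 |

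**4. How many participants.** The documents give no frequency for prompted-type events recorded only on the AE CRF. As an assumption, let the affected share p be 0.5% to 2%.

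| Assumed p | Expected per group, 45p | P(at least one in a group) |
|---|---|---|
| 0.5% | 0.23 | 20.2% |
| 1% | 0.45 | 36.4% |
| 2% | 0.90 | 59.7% |

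These figures only restate the assumed p on the scale of a group.

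**5. Size floor.** One diary unit is 0.5 cm, so units 1 to 4 are 0.5 to 2.0 cm and have no grade in SAP Table 5. Under SAP Table 7, redness of that size that does not interfere with function is mild. There is a built-in route to this: Protocol 8.3 has reactions seen in the 30-minute observation recorded as AEs.

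**The case against.** **The word only is not there.** True. The SAP sentence says what is added and does not say that unrelated events are left out. A reader might infer a stated exclusion covering all reactogenicity, and the documents do not support that: the fever and highest-grade rules omit the condition. Exclusion is the natural reading, because otherwise the qualifier does nothing, but it is an inference. Parts of 3.1.2.1 are also redacted.

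**The protocol's estimand concerns prompted events.** AE-CRF-only events are an SAP addition, and admitting unrelated ones moves further from diary collection. This has some weight. However, the SAP chose to consolidate the two sources, and its own Table 2 omits the word prompted. Having consolidated, it needs one entry rule. The diary also already admits events with another cause.

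**Other safeguards exist.** These stand and limit the point. Under SAP 6.1.2.1 the AE statistics "will be provided for any AEs, by each SOC and each PT within the SOC for each group", with no causality filter, so an event judged unrelated is still reported there. Severe, related and immediate AEs are summarised separately. Protocol 10.3.3 treats a case as related for reporting purposes "If the investigator does not know whether or not the study intervention caused the event". That does not help an event judged unrelated, and the AE table does not correct the reactogenicity percentage, which is a separate primary endpoint.

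**Open-label bias is speculative.** A reader might infer that the condition biases candidates against controls. The documents show no such bias. Protocol 2.1 argues that there are few preconceived ideas about the candidates, and participants are unblinded too, so diary entries share the exposure. The point is that an avoidable open-label judgment enters a primary endpoint, without any claim about its direction.

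**Grade 4 has little room for a causality filter.** This is largely fair for local reactions such as necrosis. It is weaker for systemic events, although the participant may have lower-grade diary entries for the same symptom.

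**Conclusion.** The point holds as a minor one. SAP 3.1.2.1 carries a causality condition that the diary, the estimand and two neighbouring SAP rules do not. On the natural reading, an investigator aware of the group decides whether an event recorded only on the AE CRF counts. The size is 2.2 points per affected participant. That the number affected is small is a judgment, since no frequency is given. All analyses are descriptive, and no decision rule in the visible text depends on it.

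The functional grading of AE-CRF redness and swelling is a real but secondary difference. It can raise rates where the causality condition can lower them, so the net direction is unknown. A reader might infer that small AE-CRF reactions should be removed to match the diary floor. The documents do not support that. Nothing visible shows that the AE CRF records a size; diameters are measured at unscheduled visits, which have their own CRF page (Protocol 8.10.3). A size cut would also drop a reaction of 2.0 cm or less that the investigator had graded moderate or severe.

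**What to change.** **Main change.** In SAP 3.1.2.1, delete the words *related to administration*, so that AE-CRF events of the prompted terms with onset on Day 1 to Day 7 are consolidated regardless of causality. This agrees with the AE-CRF fever rule and the Appendix 2 highest-grade rule.

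**Secondary change.** Keep AE-CRF redness and swelling in the count, keep the highest-grade rule, and remove nothing by size. Add a table footnote giving the number of participants per group whose redness or swelling count rests on the AE CRF alone.

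**Cost.** One deletion, one footnote and a little programming, with no change to data collection or denominators. Rates become slightly higher and will include some events with another cause, as diary entries already do. Small redness and swelling remain dependent on the form used, but visibly so.

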8.3.2.2.1. Fever

In order to record information on fever, a digital thermometer will be given to the participant with instructions on how to measure oral temperature at home. Temperature will be collected in the evening daily for 7 days following each study intervention administration (Days 1 through 7, where Day 1 is the day of study intervention administration) and at any time during the 7 days that fever is suspected. The highest temperature for each day will be recorded in the e-diary. In the event of a fever on Day 7, temperature will be collected daily until the fever has resolved (1 day of temperature $<100.4^{\circ}\text{F}$ [$<38.0^{\circ}\text{C}$]) in order to collect a

stop date in the CRF. Participants reporting a fever $>102.0^{\circ}\text{F}$ ($>38.9^{\circ}\text{C}$) will be prompted to contact the study site. Study staff may also contact the participant to obtain additional information if a temperature of $>102.0^{\circ}\text{F}$ ($>38.9^{\circ}\text{C}$) is entered into an e-diary. Temperature will be measured and recorded to 1 decimal place.

Temperatures obtained in degrees Fahrenheit will be programmatically converted to degrees Celsius for reporting. Fever will be grouped into ranges for the analysis according to Table 4.

Table 4. Ranges for Fever

$\geq 38.0^{\circ}\text{C}$ to 38.4°C
$>38.4^{\circ}\text{C}$ to 38.9°C
$>38.9^{\circ}\text{C}$ to $40.0^{\circ}\text{C}^{\text{a}}$
$>40.0^{\circ}\text{C}^{\text{a}}$

Note: Fever is defined as a temperature of $\geq 38.0^{\circ}\text{C}$.

a. Participants reporting a fever $>102.0^{\circ}\text{F}$ ($>38.9^{\circ}\text{C}$) will be prompted to contact the study site.

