If the participant reports redness or swelling at the injection site measuring >20 measuring device units (>10.0 cm) or severe injection site pain ([Section 8.3.2.1](#)), a temperature >40°C

PFIZER CONFIDENTIAL

[REDACTED]

during the 7 days following study intervention administration at Visit 1, or a severe systemic event ([Section 8.3.2.2](#)) during the 7 days following study intervention administration at Visit 1, a telephone contact must occur as soon as possible between the investigator or medically qualified designee and the participant to assess if an unscheduled investigator site visit is required. A site visit should be scheduled as soon as possible to assess the extent of the injection site reaction unless any of the following is true:

- The participant is unable to attend the unscheduled visit.
- The reaction is no longer present at the time of the telephone contact.
- The participant recorded an incorrect value in the e-diary (confirmation of an e-diary data entry error).
- The PI or authorized designee determined it was not needed.

This telephone contact will be recorded in the participant's source documentation and the CRF. If the participant is unable to attend the unscheduled visit, or the PI or authorized designee determined it was not needed, any ongoing reactions must be assessed at the next study visit. During the unscheduled visit, the reactions should be assessed by the investigator or a medically qualified member of the study staff, such as a study physician or a study nurse, as applicable to the investigator's local practice, who will:

- Measure oral temperature (°F/°C).
- Measure minimum and maximum diameters of redness (if present).
- Measure minimum and maximum diameters of swelling (if present).
- Assess injection site pain (if present) in accordance with the grades provided in [Section 8.3.2.1](#).
- Assess systemic events (if present) in accordance with the grades provided in [Section 8.3.2.2](#).
- Assess for other findings associated with the reaction and record on the AE page of the CRF, if appropriate.

The investigator or an authorized designee will complete the unscheduled visit assessment page of the CRF.

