- Prevents daily activity, eg, results in missed days of school or work or is otherwise incapacitating.

Table 6. Grading Scales for Systemic Events Collected From the E-Diary

	Mild Grade 1	Moderate Grade 2	Severe Grade 3^a	Grade 4^b
Fatigue (tiredness)	Does not interfere with activity	Some interference with activity	Prevents daily routine activity	Emergency room visit or hospitalization for severe fatigue
Headache	Does not interfere with activity	Some interference with activity	Prevents daily routine activity	Emergency room visit or hospitalization for severe headache
Muscle pain	Does not interfere with activity	Some interference with activity	Prevents daily routine activity	Emergency room visit or hospitalization for severe muscle pain
Joint pain	Does not interfere with activity	Some interference with activity	Prevents daily routine activity	Emergency room visit or hospitalization for severe joint pain

Abbreviation: CRF = case report form.

- a. Prevents daily routine activity, eg, results in missed days of school or work or is otherwise incapacitating; includes use of narcotics for analgesia.
- b. Grade 4 assessment should be made by the investigator; Grade 4 systemic events will not be collected in the e-diary but will be collected as AEs on the CRF. The intensity of the systemic event should be graded using the AE intensity grading scale.

Table 7. Assessment of AE Intensity Grade

Grade	If required on the AE page of the CRF, the investigator will use the adjectives MILD, MODERATE, and SEVERE to describe the maximum intensity of the AE. For purposes of consistency, these intensity grades are defined as follows:	
1	MILD	Does not interfere with participant's usual function.
2	MODERATE	Interferes to some extent with participant's usual function.
3	SEVERE	Interferes significantly with participant's usual function.

Document Approval Record

Document Name: C4801001 Statistical Analysis Plan V2 Clean Copy, 05Dec2022

Document Title: A PHASE 1, RANDOMIZED, OPEN-LABEL TRIAL TO EVALUATE THE SAFETY AND IMMUNOGENICITY OF PNEUMOCOCCAL CONJUGATE FORMULATIONS IN HEALTHY ADULTS 18 THROUGH 49 YEARS OF AGE

Signed By:	Date(GMT)	Signing Capacity
-------------------	------------------	-------------------------

PPD

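### The SAP converts AE-CRF fever intensity into a temperature range and then takes the highest grade across sources, so a measured temperature can be overridden upward in the primary fever table (minor)

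*SAP*

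**What the plan says.** - **Protocol 8.3.2.2.1 (Fever).** Fever is a temperature of 38.0°C or above, and "Temperature will be measured and recorded to 1 decimal place". Recorded temperatures are grouped by the Table 4 cut-offs. Intensity ratings play no part.
- **SAP 3.1.2.1.** The e-diary is named as the main source, but related events with onset within 7 days that are found on the AE CRF are merged into the reactogenicity summary. "For fever reported on the AE CRF within 7 days after administration, mild fever will be grouped in the" 38.0–38.4°C range; moderate goes to >38.4–38.9°C and severe to >38.9–40.0°C. The one stated exception is a temperature above 40.0°C noted "in an unplanned visit contact or noted on the AE CRF".
- **Note under SAP Table 4.** An indication of fever on the AE CRF is given as an alternative to e-diary data in the definition of fever.
- **SAP Appendix 2.** "For reactogenicity collected in the AE CRF, the grading scales will be based on the AE intensity scale in Table 7". The top grade in Table 7 reads "Interferes significantly with participant's usual function", and no grade in that table mentions temperature. For an event held in more than one source, the rule reads: "eg, e-diary, unplanned assessments, and/or AE CRF, the highest grade will be used in the safety summary analysis".
- **SAP 6.1.1.1.** Each systemic event is reported per group by maximum severity, with Clopper-Pearson 95% CIs.
- **SAP 2.1.** No modification of the protocol's analysis plan is declared.

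**The concern.** Table 4 holds temperature cut-offs, while Table 7 grades how far an event disturbs daily life. A participant can be in bed with 38.2°C or carry on at 39.3°C, so neither scale can be read off the other. The SAP equates the two for AE-CRF fevers and then lets the higher category win. It never says that a recorded temperature prevails.

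Fever by range belongs to the primary safety endpoint. AE intensity is rated by investigators who know the assignment (Protocol 6.4.2 and 10.3.3). For the participants concerned, an unblinded judgement of function can therefore replace an objective reading in the primary table. The protocol contains no such mapping, yet SAP 2.1 reports no change.

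**Working it through.** The plan states no figure on this point, so the check applies the derivation rule to cases and then sizes one reclassification.

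**Inputs.** The Table 4 ranges, the intensity mapping and the >40.0°C exception come from SAP 3.1.2.1. The highest-grade rule and Table 7 come from SAP Appendix 2. The group size of 45 comes from Protocol 9.5, and the exact CI method from SAP 5.2.1. The temperatures below are assumed for illustration.

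**Step 1: the rule as written.** Where the e-diary or an unplanned assessment holds a temperature, tabulated range = max(range of measured temperature, range mapped from AE-CRF rating). The comparison is the range of the measured temperature alone.

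| Measured maximum | Measured range | SAP: mild | SAP: moderate | SAP: severe |
|---|---|---|---|---|
| 37.6°C | no fever | 38.0–38.4 | >38.4–38.9 | >38.9–40.0 |
| 38.2°C | 38.0–38.4 | same | >38.4–38.9 | >38.9–40.0 |
| 38.7°C | >38.4–38.9 | same | same | >38.9–40.0 |
| 39.5°C | >38.9–40.0 | same | same | same |
| 40.2°C | >40.0 | same | same | same |

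Six of the 15 combinations depart from the thermometer, all upward: three at 37.6°C, two at 38.2°C and one at 38.7°C. The grid shows which combinations fail. It does not show how often they occur.

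**Step 2: effect on any-fever incidence.** In the 38.2°C and 38.7°C rows the participant has a fever on either rule, so only the range changes. In the 37.6°C row a fever is counted that no thermometer recorded. This follows from the Table 4 note, and also from the mapping itself, whose lowest category is already a fever range.

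**Step 3: downward error.** Appendix 2 lists unplanned assessments as a source. A reading of 39.3°C taken there lies in >38.9–40.0°C and outranks an AE-CRF entry rated mild. If 39.3°C is noted only on the AE CRF, however, the rating alone sets the range, because the only exception is for temperatures above 40.0°C. A mild rating then gives 38.0–38.4°C.

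**Step 4: size.** One participant moves a row by 1/45 = 2.2 percentage points. Exact limits at n = 45:

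- 0/45: upper limit 1 − 0.025^(1/45) = 7.9%; interval 0–7.9%.
- 1/45 = 2.2%: lower limit 1 − 0.975^(1/45) = 0.06%; interval 0.06–11.8%.
- 2/45 = 4.4%: interval 0.5–15.1%.

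**The case against.** The strongest defence is that the mapping is only a fallback for AE-CRF fevers without a temperature. SAP 3.1.2.1 calls the e-diary the main source and says that the maximum Day 1–7 temperature is mapped into Table 4. Table 6 has no fever row, so applying the highest-grade rule to fever takes a step of inference. That may well be the intent, but the SAP does not say so. Naming a main source sets no precedence when sources disagree, Appendix 2 supplies a rule for exactly that case, and SAP 3.1.2.1 lists fever among the systemic events to which it applies.

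The objections on size mostly stand. Daily e-diary data are not copied to the CRF (Protocol 8.3.1). The stated routes to the AE page are narrow: withdrawal because of prompted events (8.3.1), reactions in the 30-minute observation (8.3), and fever otherwise reported to the site as an AE. The event must also be related, begin within 7 days and carry a rating at odds with the thermometer. The study is descriptive, and an upward shift is conservative for a safety table.

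A reader might infer three stronger claims, which the documents do not support:

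- **Measured temperatures can be lowered in general.** They cannot where the e-diary or an unplanned assessment holds them (step 3).
- **A fever above 40.0°C rated moderate is downgraded.** This needs the exception to attach to severe fever alone, whereas it can be read as covering the whole mapping sentence. Even on the narrow reading, the value must be absent from every other source.
- **The fever endpoint as a whole is open to rater bias.** Only AE-CRF fever entries are exposed.

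**Conclusion.** The point holds as a minor one. Read plainly, the SAP lets an intensity rating move a measured fever into a higher Table 4 range, and lets an AE-CRF fever count when all measured temperatures are below 38.0°C. A downward error is confined to temperatures noted only on the AE CRF. Any-fever incidence is affected only in the below-38.0°C case; otherwise one range row gains a participant and another loses one.

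The documents give no expected number of AE-CRF fevers, so the total effect cannot be stated. It is 2.2 points per participant, and the narrow entry routes suggest few. The conclusion assumes that the highest-grade rule applies to fever, which is the plain reading of SAP 3.1.2.1 with Appendix 2. No sample-size or probability figure in the plan is affected.

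**What to change.** In SAP 3.1.2.1 and Appendix 2, state that:

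1. Fever and its Table 4 range are determined by the highest measured Day 1–7 temperature from any source: e-diary, unplanned assessment or contact, or AE CRF.
2. The AE-intensity mapping is used only when no measured temperature exists for that fever, and such cases are footnoted.
3. An AE-CRF fever whose measured temperatures are all below 38.0°C is listed but not counted in the fever rows.
4. For fever, the highest-grade rule compares temperatures and not AE intensity.

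Align the Table 4 note with item 3, and list the rule in SAP 2.1, because the protocol has no intensity mapping.

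The cost is about one SAP paragraph and a small programming change. Oral temperature is already collected in the e-diary and at unscheduled visits (Protocol 8.3.2.2.1 and 8.10.3), so no new data are needed. No protocol amendment is needed either, since the change brings the SAP closer to the protocol's definition.
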